The effect of U-500R begins within 30 minutes, has a peak similar to that observed with human regular U-100 insulin (U-100R), and has a relatively long duration of activity (up to 24 hours) following a single dose as compared with U-100R (de la Peña et al. 2011). Similarly, a U-500R pharmacokinetic/pharmacodynamics simulation modeling study indicated the steady-state basal pharmacokinetic/pharmacodynamics effect from both BID and TID dosing appears to support use of U-500R as insulin monotherapy (de la Peña. 2014). A recently completed randomized, controlled Phase 4 trial (B5K-US-IBHC) comparing TID versus BID U-500R monotherapy over 24 weeks in 325 subjects demonstrated that U-500R as insulin monotherapy is safe and efficacious (HbA1c reduction of 1.1% to 1.2% [Hood et al. 2015]).

Clinical expert reviews recommend MDI delivered TID injections for all dosage ranges of U-500R (Cochran et al. 2005; Lane et al. 2009; Segal et al. 2010; Reutrakul et al. 2012; Cochran et al. 2014). A number of clinical case series (Knee et al. 2003; Schwartz 2004; Lane 2006; Bulchandani et al. 2007; Lane et al. 2010; and Reutrakul et al. 2011) have also reported use of U-500R by continuous subcutaneous insulin infusion (CSII), a practice that may account for approximately one quarter of current U-500R therapy according to recent large retrospective real-world claims database analysis (Eby et al. 2014). These U-500 CSII therapy case series have shown improvements in HbA1c from 1.2% (Lane et al. 2010) to 3.5% (Knee et al. 2003), and a mean reduction of 1.64% in a review by Reutrakul et al. (2012) which reported severe hypoglycemia in 2 (n=55) subjects. The largest and longest case series (N=59; mean duration of follow up 49 months [range: 12 to 114 months]; Lane et al. 2013) reported 1.0% mean decrease in HbA1c (from 8.3% to 7.3%) sustained over 66 months of U-500 CSII therapy with severe hypoglycemia rate (defined by blood glucose [BG] ≤ 50 mg/dL or “blood glucose requiring treatment [regardless of value]”) at 0.1 episodes per patient per year.

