12.2. Statistical and Analytical Plans

12.2.1. General Considerations

Statistical analysis of this study will be the responsibility of Eli Lilly and Company or its designee.

Unless otherwise specified, both safety and efficacy analyses will be conducted on the ARS, including those who discontinued study treatment or were rescued. This set includes all randomized patients and is defined based on the intention-to-treat (ITT) principle. Sensitivity analysis may be done for the Full Analysis Set (FAS) that includes ARS subjects who received at least 1 dose of the U-500R via the administration method to which they were assigned.

Separate efficacy analyses for primary and key secondary objectives will be conducted by either including or excluding post study treatment discontinuation/data based on different FDA analyses (see Section 12.2.7). In general, missing data will not be imputed, unless otherwise specified (eg, where the multiple imputation method or the LOCF method is mentioned).

Baseline will be the last value obtained at or prior to the randomization, Visit 4 (Week 0), unless otherwise stated.

All tests of treatment effects will be conducted at a 2-sided alpha level of 0.05, unless otherwise stated.

Changes to the data analysis methods described in the protocol will require an amendment **only** if it changes a principal feature of the protocol. Any other changes to the data analysis methods described in the protocol, and the justifications, will be described in the clinical study report. Additional exploratory analyses of the data will be conducted as deemed appropriate.

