12.2.10. Safety Analyses

As stated in Section 6.2, all of the secondary objectives will be analyzed for Group A and for the total study population (Groups A and B combined). Safety measures will include hypoglycemic events, body weight, AEs and TEAEs, vital signs (systolic and diastolic blood pressures and pulse), study treatment exposure, and laboratory measures. As stated in Section 12.2.1, all safety measures will be summarized for ARS including the data after subjects discontinue study treatment and device but still remain in the study by treatment and by visit for the 26-week treatment period. Safety measures will also be listed for those patients who discontinue study treatment but still remain in the study for safety monitoring purpose. These listings will contain data after the patients discontinue the study treatment. For treatment comparisons of frequency and proportion of event variables (such as AEs and hypoglycemia events), the conventional Fisher’s exact test or Pearson’s chi-square test are appropriate to use. Further details of analyses will be provided in the SAP.

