Separate efficacy analyses for primary and key secondary objectives will be conducted by either including or excluding post study treatment discontinuation data based on different purposes (see Section 5.9 and Section 5.10). In general, missing data will not be imputed, unless otherwise specified, for example, where the Last-Observation-Carried-Forward (LOCF) method or the copy reference multiple imputation method (per FDA's request) is mentioned.

Outcomes (laboratory, vital signs, weight, patient reported outcome questionnaires) measured within 5 days of last treatment dose will be considered on treatment and included in the analysis during the treatment period.

For data collected as a running record with an exact date stamp such as adverse events (AEs), SMBG, and hypoglycemia event where the dates of the measures were not tied with the date of an office visit, post-baseline data recorded at or prior to the last study drug dose date will be considered as data on treatment and included in the analysis during the treatment period.

Baseline will be the last value obtained at or prior to the randomization, unless otherwise stated.

For continuous measurements, summary statistics will include sample size, mean, median, SD, minimum, and maximum. Summary statistics for continuous measures will be provided for baseline, the actual measurements at each visit, and the change from baseline measurements to each visit. For all continuous variables, both the actual value and change from baseline (if available) will be analyzed.

An MMRM model will be used for continuous outcomes with repeated post-baseline measurements to compare treatment arms, unless otherwise noted. An ANCOVA or analysis of variance (ANOVA) model may also be used for continuous outcomes to compare treatment arms at the endpoint using the LOCF method. Treatment comparisons will be performed for the treatment difference in least squares means (LSMean). LSMean (standard error [SE]) by treatment group and visit (if applicable), the LSMean difference between treatment groups, along with 95% confidence limits of the treatment differences and the p-value for the treatment comparison will be displayed. For the change from baseline, p-value for the within-treatment difference will also be displayed.

All tests of treatment effects will be conducted at a 2-sided alpha level of 0.05, unless otherwise stated.

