### 5.13.2.1. Hypoglycemic Analyses

Hypoglycemic analyses will be conducted on the ARS population. The same categories and subcategories defined in Section 5.13.2 will be used for summary and modeling purposes.

The hypoglycemic event rate (per 30 days and per 1 year), incidence (number) and percent of subjects reporting at least 1 hypoglycemic episode for a given treatment at certain week intervals will be summarized. The week intervals include: lead-in period (-2, 0], treatment period including (0, 2], (2 to 8], (8 to 26], (0 to 26] weeks. Note that the closed brackets will indicate to include a value/week; whereas, parentheses will indicate not to include the corresponding value/week. For example, (0 to 2] means all values between Week 0 and Week 2, including Week 2, but not including Week 0.

Treatment comparison of the incidence of hypoglycemia (documented [documented symptomatic, asymptomatic, and unspecified], severe, and nocturnal) will be done using logistic regression for each week interval, excluding poststudy treatment discontinuation data. For the analysis in Group A, the logistic model will include baseline hypoglycemia event rate for week interval (-2, 0] of the corresponding category of the dependent hypoglycemia variable standardized by 30 days (or 1 year) as covariates, treatment (U-500R CSII, U-500R MDI), and the stratification factors (U-500R at entry versus other insulins, entry HbA1c  $\geq 8.5\%$  or  $< 8.5\%$ ) as fixed effects. For the analysis in Group A+B, the stratification factor (and nonusers versus users of GLP-1 receptor agonists or SGLT2 inhibitors) will be added into the model.

For summary purpose, the rate per 30 days calculated between 2 visits is defined as the total number of episodes for all subjects between the visits divided by the total actual number of exposure days between the visits, and then multiplied by 30 days. A similar definition will be used to calculate the rate per subject per 365 days (1 year).

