The analysis approach for the rate of hypoglycemia is based on a negative binomial model with log link function, excluding post study treatment discontinuation data. The response variable is the hypoglycemic event count per visit per subject. For Group A, the model will include baseline hypoglycemia event rate for week interval (-2, 0] of the corresponding category of the dependent hypoglycemia variable standardized by 30 days as covariates, treatment (U-500R CSII, U-500R MDI), and the stratification factors (U-500R at entry versus other insulins, entry HbA1c  $\geq 8.5\%$  or  $< 8.5\%$ ) as fixed effects. For the analysis in Group A+B, the stratification factor (nonusers versus users of GLP-1 receptor agonists or SGLT2 inhibitors) will be added into the model. The logarithm of exposure days (standardized by 30 days) between visits will be used as the offset variable. In LSMeans statement, Observed Margin (OM) option will be added to specify weighting scheme for LSMean computation as determined by the input data set. The LSMean of hypoglycemia rate per 30-days by treatment for each week interval will be reported,

and the rate ratio between treatments will also be presented. Wilcoxon signed-rank test may be performed as sensitivity analysis.

The 1-year rate of documented symptomatic and severe hypoglycemia (with BG  $\leq$ 70 mg/dL) for every 2-hour interval (0:00-1:59, 2:00-3:59, 22:00-23:59) over the 26 week post-randomization period will be summarized. The rate of hypoglycemia will also be analyzed using a negative binomial model. The response variable is the hypoglycemic event count per 2-hour interval per subject. The analysis approach will be similar to the hypoglycemia rate analysis approach above for Group A and Group A+B.

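### Both hypoglycemia comparison models in the SAP drop data after treatment discontinuation, which the protocol says its safety summaries include, and no all-data comparison is planned

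*SAP*

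**What the plan says.** **Protocol.** Section 12.2.10 lists hypoglycemic events among the safety measures and states that "all safety measures will be summarized for ARS including the data after subjects discontinue study treatment and device but still remain in the study". The breakdown is per arm and per visit, over the 26 weeks. The synopsis repeats this. Section 12.2.1 says that "both safety and efficacy analyses will be conducted on the ARS, including those who discontinued study treatment or were rescued". Its provision for analyses with and without later data is worded for efficacy: "Separate efficacy analyses for primary and key secondary objectives will be conducted by either including or excluding post study treatment discontinuation". Section 12.2.10.1, which sets out the hypoglycemia tests, contains no on-treatment restriction.

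**SAP.** Section 5.13 keeps the all-randomized population for safety summaries but omits the protocol's clause on post-discontinuation data. It says only that any listings will contain them. In Section 5.13.2.1 the logistic model for incidence is fitted "excluding poststudy treatment discontinuation data", and the rate analysis uses a "negative binomial model with log link function, excluding post study treatment discontinuation data". For date-stamped records such as hypoglycemia, Section 5.2 adds that "post-baseline data recorded at or prior to the last study drug dose date will be considered as data on treatment".

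Hypoglycemia rate and incidence are a named secondary objective for Group A and for Groups A and B combined (Protocol 6.2.2, SAP 4.2.2).

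**The concern.** The protocol asks subjects who stop study treatment to remain in the study so that their safety can be followed. The SAP then uses none of that follow-up in either hypoglycemia comparison.

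The cut is not neutral. Protocol 8.3.2 stops study treatment when exclusion criterion [11], more than one severe hypoglycemia episode, is observed or develops after enrollment. A subject can therefore leave the models because of the outcome being modeled, and the chance of this may differ between pump and injections. A comparison truncated in this way is no longer protected by randomization. It answers a reasonable on-treatment question, but it cannot stand in for the comparison of all randomized subjects over 26 weeks.

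**Working it through.** **1. The texts side by side**

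| Item | Protocol | SAP |
|---|---|---|
| Safety summaries | All randomized, post-discontinuation data included (12.2.10) | All randomized; inclusion clause absent (5.13) |
| With/without split | Efficacy only (12.2.1) | Efficacy split kept (5.2); exclusion also applied to hypoglycemia (5.13.2.1) |
| Incidence comparison | No restriction (12.2.10.1) | Post-discontinuation data excluded |
| Rate comparison | No restriction (12.2.10.1) | Post-discontinuation data excluded |
| Descriptive rate and incidence tables | Included (12.2.10) | Not stated in 5.13.2.1; 5.2 points to on-treatment data |
| Listings | Included | Included where listings are provided (5.13); SAE listing includes them (5.13.3) |

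**2. How much follow-up could be excluded**

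The documents give no figure, so this is an illustration. The only planning input is the 25% dropout rate, which the sample-size section reproduces: 320 × (1 − 0.25) = 240 completers in Group A.

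Assumptions: 25% of subjects stop treatment (0.25 × 320 = 80, or 40 per arm); the mean stopping week *m* is 4, 13 or 22; a fraction *f* of those who stop stay to Week 26, and the rest give no data after stopping.

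- Excluded days = 80 × *f* × (26 − *m*) × 7
- On-treatment days = 240 × 182 + 80 × *m* × 7
- Share = excluded ÷ (on-treatment + excluded)

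For *m* = 13 and *f* = 0.5: excluded = 80 × 0.5 × 13 × 7 = 3,640; on-treatment = 43,680 + 7,280 = 50,960; share = 3,640 ÷ 54,600 = 6.7%.

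| Fraction staying | *m* = 22 | *m* = 13 | *m* = 4 |
|---|---|---|---|
| 0 | 0% | 0% | 0% |
| 25% | 1.0% | 3.4% | 6.3% |
| 50% | 2.0% | 6.7% | 11.8% |
| 100% | 3.8% | 12.5% | 21.2% |

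The shares are the same for Groups A and B combined, because every term scales with the number randomized. These are shares of follow-up time, not of events. The event rate after stopping is unknown.

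**3. The day after the last dose**

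One extra day for each of the 80 subjects, divided by on-treatment days, is 80 ÷ 56,000 = 0.14% (*m* = 22) to 80 ÷ 45,920 = 0.17% (*m* = 4). This is very small next to the main exclusion whenever an appreciable number of subjects stay.

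**4. The denominator**

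SAP 5.13.2.1 uses log exposure days between visits as the offset, and SAP 5.13.1 measures exposure from first to last dose. Suppose a subject stops at Week 13 and is followed to Week 26. Counting 182 days of events against 91 days of exposure would double that subject's rate if events were constant over time (182 ÷ 91 = 2). A visit interval wholly after the last dose would have zero exposure, for which the log is undefined. An all-data rate model therefore needs its own offset.

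**The case against.** The strongest reply is that the protocol promises summaries, not models. Section 12.2.10 names no model, and the all-randomized rule in 12.2.1 can be read as fixing which subjects are analyzed, not which of their days. The protocol's rate formula divides by exposure days, which can itself be read as time on treatment. The exclusion in SAP 5.13.2.1 is attached to the two models and not to the descriptive tables. This stands in part: a reader might infer that the promised events disappear altogether, and the documents do not show that. The SAP leaves the data cut of the descriptive tables unclear. Severe hypoglycemia is an SAE by definition, and the SAE listing keeps events after discontinuation. None of this supplies a treatment comparison that includes those data.

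Three other inferences are tempting and not supported:

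- **An undisclosed change.** The revision history does not list this exclusion, but it compares two SAP versions, and version 1 is not available. Whether the exclusion was new is unknown. Both documents also send other departures from protocol methods to the study report.
- **Loss of next-night events as a main defect.** Protocol 5 says U-500R "has a relatively long duration of activity (up to 24 hours) following a single dose", so an event after midnight could fall outside the last-dose-date rule. However, that describes a single dose, the volume is about 0.15% of on-treatment days, and the SAP does not say that the discontinuation date equals the last dose date. The contrast with laboratory, vital-sign, weight and questionnaire data "measured within 5 days of last treatment dose will be considered on treatment" is not like with like, because the SAP separates records that are not tied to an office visit.
- **25% as a ceiling.** It is a planning rate for dropout. It can be exceeded, and it includes subjects who leave the study and give no later data.

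**Conclusion.** The point holds as a protocol–SAP conflict with a consequence for a secondary safety objective. The protocol says hypoglycemia is summarized with post-discontinuation data and gives no on-treatment restriction for its tests. The SAP excludes those data from both of its modeled comparisons and specifies no comparison that includes them. An on-treatment model is legitimate; the defect is that it is the only one.

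The size is not determined by the documents. With 25% stopping treatment, the excluded share runs from 0% if none stay to 21.2% if all stay and stop at Week 4 on average. The direction of any bias is also unknown, because it depends on how stopping relates to hypoglycemia in each arm. The primary HbA1c analysis, sample size and power are unaffected.

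**What to change.** 1. Keep the two on-treatment models and label them as such.
2. Add incidence and rate comparisons, for Group A and for Groups A and B combined, on all data from all randomized subjects up to the last study visit (at most Week 26). In the negative binomial model, define the offset as observed days over the same period in which events are counted, not as first-to-last-dose exposure.
3. State in SAP 5.13.2.1 that the descriptive rate and incidence summaries include post-discontinuation data, as Protocol 12.2.10 requires, and restore that clause in SAP 5.13.
4. Optional and minor: allow a 1-day lag after the last dose for date-stamped events in the on-treatment models, with the offset extended by the same day.

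The cost is SAP wording and one more set of hypoglycemia tables from data already collected on subjects who stay. The downside is interpretive: events after discontinuation may reflect non-study insulin, which is why both sets should be shown side by side.

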12.2.7. Primary Outcome and Methodology

The primary efficacy measure is change from baseline to the 26-week HbA1c value. The primary analysis will be conducted for the All Randomized Set (ARS) population in Group A. There will be two primary analysis methods for different purposes as follows:

1. Per FDA’s request, the analysis method will use the copy reference approach to impute missing data based on multiple imputations with a pattern mixture model (later referred to as ‘copy reference multiple imputation analysis’). This analysis will include post study treatment discontinuation data. The reference is all observed data from all randomized subjects in the same treatment arm who discontinued study treatment but completed the study without missing data. After imputation, an analysis of covariance (ANCOVA) with baseline HbA1c as a covariate, treatment (U-500R CSII, U-500R MDI) and the stratification factor

(U-500R at entry versus other insulins) as fixed effects will be used to analyze the 26-week HbA1c including imputed values.

If in the reference group mentioned above there is only a limited number of subjects and this leads to a failure in performing the proposed multiple imputation analysis, the reference will be changed to include all observed data from all randomized subjects in the same treatment arm who do not have missing data.

2. For manuscripts and other non-FDA submission purposes, a MMRM model that does not include post study treatment discontinuation data and adjusts for missing data through an observed-data-likelihood-based approach will be used. The model will include the following fixed effects: treatment (U-500R CSII, U-500R MDI), weeks on treatment, the interaction between treatment and weeks, and the stratification factor (U-500R at entry versus other insulins). The model will also include baseline HbA1c as a covariate.

As a sensitivity analysis to the missing at random assumption of MMRM model, a stress test will be performed. The missing data are first imputed with the missing at random assumption. Prior to multiple-imputation analysis, in the CSII arm the imputed values will be replaced by the imputed value plus delta. Multiple values of delta within a clinically reasonable and meaningful range will be tested to assess if the conclusion from the MMRM primary analysis changes.

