12.2.10.1. Hypoglycemia

The rate per 30 days calculated between 2 visits is defined as the total number of episodes for all subjects between the visits divided by the total actual number of exposure days between the visits, and then multiplied by 30 days. A similar definition will be used to calculate the rate per subject per 365 days (year).

For documented (documented symptomatic, asymptomatic and unspecified), severe and nocturnal hypoglycemic episodes, the following analyses will be conducted. The incidence and percentage of subjects with at least 1 hypoglycemic event will be analyzed using Fisher’s exact test or Pearson’s chi-square test, as appropriate. The rate of hypoglycemic events per 30 days

and per 365 days will be analyzed using a negative binomial regression model with similar fixed effects as in the primary MMRM analysis model. Baseline hypoglycemic event rate for the corresponding category of the dependent hypoglycemia variable will be included as a covariate, as well as the stratification factors.

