For the MMRM model, the Kenward-Roger approximation will be used to estimate denominator degrees of freedom. An unstructured covariance matrix will be used to model the within-subject errors. If the unstructured covariance configuration results in a lack of convergence, then the following variance-covariance matrix will be used (in order) until one converges:

Heterogeneous Toeplitz; Heterogeneous First Order Autoregressive; Heterogeneous Compound Symmetry; Toeplitz; First Order Autoregressive; Compound Symmetry. If all variance-covariance matrices selected fail to converge, Variance Components will be used as the next attempt at convergence.

The test for the primary objective of non-inferiority will be performed at the 0.05 significance level using the LSMean estimate of the difference in change in HbA1c between the 2 treatments

at Week 26. Non-inferiority will be established if the upper limit of a 2-sided 95% confidence interval (CI) for the difference (U-500R CSII minus U-500R MDI) is below the NIM of 0.4%.

Using the LSMean estimate of the difference in change in HbA1c between the 2 treatments, superiority will be established if the upper limit of a 2-sided 95% CI for the difference (U-500R CSII minus U-500R MDI) is below 0.

The following supportive and sensitivity analyses will also be conducted:

- If the following sets are different from ARS, then similar copy reference multiple imputation and MMRM analyses will be done for the FAS (subjects who were randomized and received at least 1 dose of the study insulin through the administration method they were assigned to), all completer set (subjects who complete the study treatment), and the per-protocol population (subjects included in the ARS who have completed the study without important protocol deviations that will impact the primary outcome).
- An ANCOVA model with similar fixed effects as in the copy reference multiple imputation analysis using LOCF method for the ARS will also be performed.
- For the analysis performed for the ARS population for Groups A+B, the analysis model will include an additional stratification factor (nonusers versus users of GLP-1 receptor agonists or SGLT2 inhibitors) as a fixed effect.

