### 5.10. Secondary Outcomes and Analyses

For Group A and Group A+B in the ARS population, similar to the primary analysis, 2 sets of analysis approaches (copy reference multiple imputation and MMRM) will be used to analyze the change from baseline for the following key secondary endpoints 1 and 2 at Week 26. For endpoint 3, only MMRM analysis will be performed.

- 1) FPG (by laboratory measurement)
- 2) 7-point SMBG
- 3) total daily insulin dose (TDD)

For Group A, the MMRM model will include the following fixed effects: treatment (U-500R CSII, U-500R MDI), weeks on treatment, the interaction between treatment and weeks, and the stratification factors (U-500R at entry versus other insulins, entry HbA1c  $\geq 8.5\%$  or  $< 8.5\%$ ). The model will also include the corresponding baseline of the response variable. For the copy reference approach, the ANCOVA model will include the following fixed effects: treatment (U-500R CSII, U-500R MDI), the stratification factors (U-500R at entry versus other insulins, entry HbA1c  $\geq 8.5\%$  or  $< 8.5\%$ ) and the corresponding baseline measures.

For Group A+B, the same MMRM model and ANCOVA models in Group A above will be used with the addition of the stratification factor (nonusers versus users of GLP-1 receptor agonists or SGLT2 inhibitors).

For SMBG, the average of the 2 non-consecutive-day values for scheduled visits will be used.

Total daily dose will be calculated as the sum of maximum total bolus dose and basal dose at each visit. The maximum total bolus dose of the 3 days prior to each scheduled visit for each subject will be used to calculate the TDD value for data summary and statistical analysis to avoid the underestimated TDD due to missed meal(s). The basal dose will be only collected for 1 day prior to each visit and used to calculate TDD for each visit. Body weight at each visit will be used for TDD (units/kg) calculation. Summary statistics will be done for both actual values and change from baseline (CFBL) values. The percentages of bolus and basal doses from TDD in the U-500R CSII group will be summarized by visit.

Similar to the primary analysis, 2 sets of analysis approaches (repeated-measure [or longitudinal] logistic regression excluding post study treatment discontinuation data and the multiple imputations based logistic regression including post study treatment discontinuation data) will be applied to assess the following secondary objectives in the following values at Week 26:

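### The hypoglycemia rate model is set on per-visit counts with no within-subject term; fitted that way, rate-ratio standard errors are too small for frequent events over the longer intervals

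*SAP*

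**What the plan says.** SAP 5.13.2.1 specifies a negative binomial model with log link, on data up to discontinuation of study treatment. On the unit of analysis: "The response variable is the hypoglycemic event count per visit per subject". On the offset: "The logarithm of exposure days (standardized by 30 days) between visits will be used as the offset variable". The listed terms are the lead-in event rate, treatment and the stratification factors, and nothing else. On output: "The LSMean of hypoglycemia rate per 30-days by treatment for each week interval will be reported". The intervals in weeks are (0, 2], (2 to 8], (8 to 26] and (0 to 26].

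In the same section, the incidence comparison "will be done using logistic regression for each week interval, excluding poststudy treatment discontinuation data".

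Other endpoints have their within-subject structure named. For the primary MMRM (SAP 5.9): "An unstructured covariance matrix will be used to model the within-subject errors". For the HbA1c targets (SAP 5.10): "repeated-measure [or longitudinal] logistic regression excluding post study treatment discontinuation data". The CGM model in SAP 7.4 has a random subject effect.

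Protocol 12.2.10.1 says the rate "will be analyzed using a negative binomial regression model with similar fixed effects as in the primary MMRM analysis model". Those effects (Protocol 12.2.7) include "weeks on treatment, the interaction between treatment and weeks". The SAP rate model has no week terms.

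**The concern.** Counts from one person at successive visits are positively correlated: some people have many low readings throughout, others almost none. The negative binomial dispersion parameter absorbs extra variation within a row, not correlation between rows. If each visit is a row and nothing links rows from the same subject, the model sees up to 13 independent pieces of information where there is much less.

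The rate ratio stays about right, but its confidence interval is too narrow and its p-value too small. That could produce a spurious difference between CSII and MDI in either direction, on a stated safety objective for an investigational delivery system, in both Group A and Group A+B.

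Two smaller points sit in the same section. The 2-hour analysis does not say whether each interval is fitted separately. The optional sensitivity test, Wilcoxon signed-rank, is a paired or one-sample test and cannot compare two parallel arms.

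**Working it through.** **1. The plan's own figures.** None is given for the rate model. The sample size is for HbA1c noninferiority and reproduces: 2 × 1.1² × (1.96 + 0.84)² / 0.4² ≈ 119 per arm, or 238 against the stated 240; 320 × 0.75 = 240. It does not depend on the rate model.

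**2. Rows per subject** (Protocol Attachment 1). Visits after randomization fall at weeks 1, 2, 3, 4, 6, 8, 10, 12, 14, 17, 20, 23 and 26. Office visits are weeks 1, 2, 3, 8, 14, 20 and 26.

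| Interval (weeks) | All visits | Office only |
|---|---|---|
| (0, 2] | 2 | 2 |
| (2 to 8] | 4 | 2 |
| (8 to 26] | 7 | 3 |
| (0 to 26] | 13 | 7 |

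**3. Analytic check, no covariates.** Let subjects share a gamma effect with variance k, let μ be the expected count in a visit row, and let w = 1/(1 + kμ). Per subject, A = Σμw and B = Σμw² + k(Σμw)². The model-based variance is proportional to 1/A and the true variance to B/A², so true SE / model SE = √(B/A).

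Example, assuming 15 events per year, k = 1 and 13 rows (four of 7 days, five of 14, four of 21):
- μ = 0.288, 0.575, 0.863 and w = 0.777, 0.635, 0.537.
- A = 4(0.223) + 5(0.365) + 4(0.463) ≈ 4.57.
- Σμw² ≈ 2.85, so B ≈ 2.85 + 4.57² ≈ 23.8.
- √(23.8/4.57) ≈ 2.28. Type I error = 2[1 − Φ(1.96/2.28)] ≈ 0.39.

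Over (0 to 26], with k from 0.5 to 2, the ratio is 1.01 to 1.04 at 0.1 events per year, 1.42 to 2.05 at 5, and 2.28 to 3.01 at 30.

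**4. Simulation with the SAP's covariates.** There were 160 subjects per arm (Group A as randomized), no true difference and 2000 runs per setting. Covariates were the 14-day lead-in rate, treatment and two binary strata. Assumed inputs were 0.3, 1 or 3 events per 30 days, between-subject variance 0.25, 0.5, 1 or 1.5, and extra visit-level variance 0 or 1: 24 combinations. The ratio below is mean model SE divided by the empirical SD of the log rate ratio, so below 1 is too small. Monte Carlo SE of the error is about 0.005 at 0.05 and 0.011 at 0.44.

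| Interval | Rows | SE ratio | Type I error |
|---|---|---|---|
| (0 to 26] | 13 | 0.40–0.87 | 0.09–0.44 |
| (0 to 26] | 7 | 0.50–0.89 | 0.08–0.33 |
| (8 to 26] | 7 | 0.50–0.92 | 0.07–0.33 |
| (8 to 26] | 3 | 0.65–0.93 | 0.07–0.21 |
| (2 to 8] | 4 | 0.68–0.99 | 0.05–0.19 |
| (2 to 8] | 2 | 0.82–1.01 | 0.045–0.10 |
| (0, 2], 0.3 per 30 days | 2 | 0.93–0.985 | 0.046–0.065 |
| (0, 2], 3 per 30 days | 2 | 0.85–0.98 | 0.056–0.10 |

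Example at 1 event per 30 days, variance 1, 13 rows and no visit noise: model SE 0.054, true SD 0.108, error 0.33. The 95% limits come out as the rate ratio times or divided by exp(1.96 × 0.054) = 1.11, when the data support exp(1.96 × 0.108) = 1.24.

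**5. What cures it and what does not**, over (0 to 26]:
- One summed row per subject: ratio 0.95 to 1.03, error 0.04 to 0.065, all 24 settings.
- Visit rows with subject-clustered SE: ratio 0.97 to 1.02, error 0.04 to 0.06.
- Visit main effects added to 13 rows (variance 1, 1000 runs): ratio still 0.42 to 0.64, error 0.22 to 0.43. Week terms do not remove the correlation.
- The plan's 25% dropout, with uniform times assumed (variance 1, 1000 runs): 13 rows 0.43 to 0.68, error 0.18 to 0.41; one row 0.96 to 1.01, error 0.05 to 0.06.

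A separate simulation (200 runs) at 15 per year, k = 1 and 13 rows gave SE 0.057 as written, 0.106 clustered and 0.108 summed, against an SD of 0.114 for the as-written estimate.

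**6. Rare events.** Protocol Section 5 cites 0.1 severe episodes per patient-year in a case series with a different definition (0.1 × 30/365 = 0.0082 per 30 days). There, 13 rows give 0.91 to 0.95 and one row 0.93 to 0.96, with error 0.03 to 0.04 for both, so the choice of rows makes no difference. About 1400 of 2000 runs were usable, mainly because the lead-in covariate was all zero in the rest.

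**The case against.** The strongest reply is that one summed count per subject per week interval was meant all along. The rate model has no week terms, while the SAP's MMRMs on the main study's endpoints list them. Without a week term, a rate for each interval needs a separate fit, and (0 to 26] overlaps the other three in any case. The incidence model next to it is fitted that way. The interval bounds 0, 2, 8 and 26 are themselves visits, so exposure between visits can mean exposure between the bounding visits. The protocol's amendment summary also shows the repeated-measure label being removed from this model.

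This is a reasonable account of intent, and on that reading the standard errors are adequate. It does not rescue the wording: a count per visit per subject is not a count per interval, and removing the repeated-measure label does not say that counts are summed. A programmer following the text builds visit rows in a model no longer described as repeated-measures.

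Three further points stand as limits. The SAP names no standard-error estimator, so the inflation needs visit rows and model-based errors together. The upper error of 0.44 needs the highest assumed rate and variance, 13 rows and no visit noise. If rows follow office visits, when diary data are transferred to the case report form, the problem is smaller but remains. The 2-hour outcome most naturally means one row per subject per interval, so that point only asks for clarity.

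**Conclusion.** The concern holds. As written, the outcome is a visit-level count with nothing to account for repeated rows from a subject. Fitted that way with model-based errors, the CSII versus MDI rate ratio is reported too precisely. Over (0 to 26] with 13 rows the standard error is 0.40 to 0.87 of its true value; with 7 rows, 0.50 to 0.89. The effect is smaller in (2 to 8], negligible in (0, 2] at low rates, and absent for severe events at the cited rate. The direction follows whenever a subject's counts remain positively correlated after adjustment. The size depends on assumed rates and between-subject variance, which the documents do not give for documented events.

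The crude rates, the incidence model, H1 to H10, alpha control and the sample size are not affected. On the one-row reading no bias arises, but the text still needs correcting. It should be settled before the study team has treatment assignments, because the choice can change a p-value.

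**What to change.** Preferred: in SAP 5.13.2.1, define the outcome as the total number of events per subject in the week interval, with the log of that subject's total exposure in the interval as offset, fitted separately for each interval.

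Alternative: keep visit rows, add a visit term, and declare subject as the cluster or repeated effect with robust standard errors.

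For the 2-hour analysis, state that each interval is fitted separately with one row per subject. Replace the signed-rank test with the Wilcoxon rank-sum test on subject-level rates.

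The cost is a few sentences and a small programming change, with no new data. Compared with a visit-row fit, confidence intervals for the frequent categories become wider, which is the correct width.
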